Clinical Study Protocol

Study Title: Impact of Providing Medical Records in a Patient-Centered, Community Pharmacy Based, HIV Care Model (HIV-MOI) of the Community Pharmacy-Based HIV Care Model study

ClinicalTrials.gov Identifier: NCT03437694

Sponsor: National Institute on Minority Health and Health Disparities

Sponsor Project Title: Texas Center for Minority Health, Education, Research and Outreach

FAIN Number: U54MD006882

IRB Number: 1436643/2018-094

Protocol Version/Date: Original Approval: 5/24/2019
Most Recent Approval: 10/17/2023

North Texas Regional Institutional Review Board (NTRIRB)

University of North Texas Health Science Center

PROTOCOL INFORMATION

Title of Research Activity: Medical record based versus non-medical record based community pharmacy provided medication therapy management

Name of Principal Investigator: [name], PharmD, BCIDP, BCPS (formerly known as [name])

Institution: UNTHSC

Sponsoring Agency / Company (if applicable): NIMHD

Sponsor's Protocol Number (if applicable): ClinicalTrials.gov Identifier: NCT03437694

Specific Aims –

- A. To investigate the change in control of diabetes and/or hypertension in adult African-Americans with HIV, who receive medication therapy management (MTM) from their community pharmacist when the pharmacist is provided the information from the participants' medical records (intervention) or not provided the information from the medical records (control, standard of care is no medical record information is provided). Control will primarily be determined using HgbA1c & plasma glucose from medical records (diabetes), and systolic blood pressure from medical records (hypertension) and these will be compared against nationally accepted standards for each condition. Control of HIV will be monitored (no change anticipated) via medical record provided HIV-RNA viral loads and CD4 counts.

Protocol version 9 October 2023

Medical record vs. Non-medical record

community pharmacy based MTM study

Page 1 of 31

B. Background and Significance

[figure not shown]

Figure 1: Adapted from Ribaudo 2016

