2) **Data Analysis and Data Monitoring** – Describe plans for statistical analysis of data when appropriate. If a data safety monitoring committee is appropriate to protect the safety and/or welfare of subjects, describe its operation (e.g., membership, stopping rules and frequency of review).

The diseases being used to validate HIV-CMTM effectiveness are HIV, DM and HTN. For HIV, disease control is defined as plasma HIV-RNA of < 20 copies/mL. Standard of care recommends follow-up based on viral load. (19) For DM, self-monitoring of blood glucose is less reliable than quarterly A1c levels (goal of \leq 7%) which is monitored every 3 months. In HTN, goals vary based on comorbid conditions as follow-up varies with medications. As AA have 2-3 higher incidental rates of stroke compared to whites. (Howard). As a 10 mmHg difference in systolic blood pressure is shown to reduce stroke rate by 24% in AA, a decrease in systolic blood pressure reductions of 10 mmHG [or attainment of blood pressure goal] was selected as the primary measure for effectiveness on HTN. Medical record blood pressure will be the primary source for analyses as ultimately, it is the information collected by the diagnostician that is used for decisions.

Two sample t-test for continuous outcomes (viral loads) and chi-square for categorical outcomes (blood pressure under control or not) would be used to assess significance at the 0.05 level.

DATA AND SAFETY MONITORING PLAN

There are no medical procedures or prescription changes that can occur as part of this study that are not first authorized by the patient's medical provider. A data safety monitoring plan has been presented and approved by the NIMHD Program and Science Officer that reflects the low safety risk to participants, from a medical perspective. The **DATA SAFETY PLAN** is attached. The risks to participants due to protection of information and how information is safely maintained is addressed elsewhere in the protocol.

3) **Data Storage and Confidentiality**

Data Security, Collection, Entry, Management, and Quality Control: Only authorized study personnel will have access to the data. All HIPAA research safeguards and protocols for protected health information will be observed. All randomized participants will be assigned a unique identification (UID) number for use throughout the project. This number will be

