Two hundred adult AA with HIV and either/both DM or HTN will be recruited using NTRIRB approved recruitment materials. Once consented, patient gender and comorbidity stratified randomization (i.e., separate randomization by men/women and by DM/HTN) will be used to randomize them into the intervention group or control. Randomization assignment will be controlled by the biostatistician. This will create eight groups: men with DM receiving intervention (1.a.), men with DM receiving control (2.a.), women with DM receiving intervention (1.b.), etc. (Figure 4). Patients with dual diagnosis of DM and HTN will be randomized into either the intervention or control group. Their data will be used in both DM and HTN analyses (after conducting a sensitivity analysis to determine that the dual diagnosis does not confound or bias the results). A random number generator (range 1 to 10,000) will be used for group assignment. UNTHSC biostatistician will be the only unblinded member of the research team to which number corresponds to the intervention or control groups when presenting data during investigator team safety reviews and data safety monitoring plan described.

The primary endpoint for this study will be the health indicators collected at the final follow-up visit comparing the corresponding intervention and control groups (e.g., intervention vs. control for men with diabetes). We computed the power and sample size based on the effect sizes estimated from our previous CDC-funded demonstration project where observations from 201 African American HIV patients at baseline whose viral loads were either detectable (>20 copies/mL) or their CD4 counts were <200 cells/mcL at baseline. Of these, 171 (85%) showed improvement (viral loads became undetectable or CD4 counts became >200 cell/mcL) at follow-up after receiving quarterly HIV-CMTM. Based on these results and even assuming a very conservative effect of 45% improvement for the control group receiving standard of care projects that a comparison between intervention and control will require 22 subjects per group. This enrollment volume enables attaining a power of at least 80% at the 0.05 level of significance for each of the comparisons. As some attrition is expected, we will recruit 25 patients per group for a total of 200 patients. We also note that the sample sizes are very likely larger as the subjects with a dual diagnosis of diabetes and hypertension will be included in the analyses, but are not included in the

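### HIV is only monitored in Aim A, but it is an effectiveness disease in Section E.2 and the basis of the sample size in Section F.1, which leaves a third unadjusted route to an effectiveness claim

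*Combined protocol and SAP*

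**What the plan says.** Three sections give HIV three different roles.

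- **Section A (Specific Aims).** The question is control of diabetes and hypertension. On HIV: "Control of HIV will be monitored (no change anticipated) via medical record provided HIV-RNA viral loads and CD4 counts".
- **Section E.2 (Data Analysis and Data Monitoring).** "The diseases being used to validate HIV-CMTM effectiveness are HIV, DM and HTN". The next sentence gives a binary definition: "For HIV, disease control is defined as plasma HIV-RNA of < 20 copies/mL". The test sentence then uses viral load as its example of a continuous outcome: "Two sample t-test for continuous outcomes (viral loads) and chi-square for categorical outcomes (blood pressure under control or not"), and adds that these "would be used to assess significance at the 0.05 level".
- **Section F.1 (Sample Size).** "The primary endpoint for this study will be the health indicators collected at the final follow-up visit comparing the corresponding intervention and control groups". The indicators are not named. The only effect size shown is an HIV one, from 201 participants in the earlier demonstration project: "Of these, 171 (85%) showed improvement (viral loads became undetectable or CD4 counts became >200 cell/mcL) at follow-up". The comparator is set by "assuming a very conservative effect of 45% improvement for the control group receiving standard of care", which leads to 22 per group, or 25 after attrition, in eight groups.

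The documents supplied contain no ranking of the three diseases, no multiplicity rule, and no margin or confidence-interval criterion for HIV.

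**The concern.** An outcome that is expected not to change and an outcome that is meant to demonstrate effectiveness need different analyses and support different conclusions. Section E.2 puts HIV in the second class, while Aim A puts it in the first. With no ranking or adjustment, a significant viral-load difference could be reported as validating the intervention on a disease where the stated aim expects no effect. If the role is settled only after results by arm are known, it can depend on what they show.

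Two further inconsistencies follow. Control is defined as a threshold, but the named test compares mean viral load, so the HIV measure itself is not fixed. The sample size rests on a 40-point HIV difference, although Aim A expects no HIV change and asks about two other diseases.

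**Working it through.** **1. The plan's own figure.** Inputs from Section F.1: 85% (171/201 = 0.851) against 45%, level 0.05, power at least 80%. I assume a two-sided test, pooled variance and no continuity correction. The mean rate is (0.85 + 0.45)/2 = 0.65.

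n = [1.96·√(2·0.65·0.35) + 0.842·√(0.85·0.15 + 0.45·0.55)]² / 0.40² = (1.322 + 0.515)² / 0.16 ≈ 21.1, rounded up to 22.

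Power at 22 per group is 81.7%. The stated 22 reproduces. The arithmetic is sound, but the outcome it describes is HIV improvement. Section F.1 mentions further power analyses for continuous outcomes but gives no inputs or results, so nothing shown establishes power for diabetes or hypertension.

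**2. What a third test adds.** The inputs are 0.05 per test (Section E.2) and no adjustment. Assume one test per disease, independence and no true effects.

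| Counted as a false positive | Diabetes + hypertension | Adding HIV |
|---|---|---|
| Either direction | 1 − 0.95² = 9.75% | 1 − 0.95³ = 14.3% |
| Favouring the intervention only | 1 − 0.975² = 4.9% | 1 − 0.975³ = 7.3% |

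The second row bears on false claims of effectiveness. HIV adds about 2.4 points there and about 4.5 points in either direction.

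**3. Sensitivity.** The HIV test uses the same people as the other two, and participants with both diagnoses enter both disease analyses (Section F.1), so independence is doubtful. By simulation with correlation 0.5 between test statistics, the either-direction figures are 9.1% and 12.6%, and the favourable-only figures are 4.6% and 6.3%. In the other direction, if every disease were tested separately in men and women (four tests becoming six), the independent either-direction figures would be 1 − 0.95⁴ = 18.5% and 1 − 0.95⁶ = 26.5%. The documents give neither the number of tests nor their correlation.

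**4. What one pooled HIV estimate would deliver.** Every participant has HIV (inclusion criteria), so the whole trial can contribute: 4 × 25 = 100 per arm as recruited, or 4 × 22 = 88 per arm after the attrition implied by Section F.1. The documents give no suppression rate for this population, so I assume 80% to 90%, equal in the two arms. Approximate 95% half-width, unstratified: 1.96·√(2p(1−p)/n).

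| Assumed suppression | 100 per arm | 88 per arm |
|---|---|---|
| 80% | 11.1 points | 11.8 points |
| 85% | 9.9 points | 10.6 points |
| 90% | 8.3 points | 8.9 points |

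Missing records widen these intervals. Section E.1 keeps participants in the study when records do not arrive. Enrolment was complete by 31 October 2022 and visits end on 15 December 2023, so the last enrolled have roughly 13.5 months of follow-up rather than two years.

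**The case against.** The strongest objection is that Aim A need not be the version that governs. Section F.1 sizes the trial on viral load and CD4 improvement, and Section C presents virologic suppression as promising preliminary evidence. The sponsor may want HIV as an effectiveness outcome. This stands as far as it goes: it shows that the role is unsettled, and that editing one sentence in Section E.2 would not be enough. It does not remove the contradiction.

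Several stronger readings are tempting, and the documents do not support them.

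- A reader might infer that a non-significant viral-load test will be reported as proof that HIV control was kept. No section says so. An expectation of no change is not a stated non-inferiority or equivalence objective.
- A reader might infer a declared superiority claim for HIV. The term is not used; the text only lists HIV under effectiveness and tests viral load for significance.
- A reader might take 14.3% as the chance of a false claim for the intervention. It counts both directions; the favourable-only figure is 7.3%.
- A reader might infer that HIV will be tested within sex-by-disease groups. Section F.1's example is men with diabetes, and no section assigns the HIV analysis to those groups.

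**Conclusion.** The inconsistency is real and should be corrected. HIV has incompatible roles in Sections A, E.2 and F.1, and its measure is binary in one sentence of E.2 and continuous in another. As written, it is a third unadjusted route to an effectiveness claim. The added risk is modest: 9.8% to 14.3% in either direction, or 4.9% to 7.3% in favour of the intervention. Both comparisons assume one independent test per disease, and the figures are lower with positive correlation. Taking HIV out of the effectiveness set does not deal with the remaining 9.8% for diabetes and hypertension, which is also unadjusted.

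The sample-size arithmetic is correct. What does not follow is that 22 per group gives 80% power for diabetes or hypertension, because the rates used describe HIV. They also come from people with detectable virus or a low CD4 count at baseline, which is not an entry criterion here.

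**What to change.** Give HIV one role in Sections A, E.2 and F.1, dated before any comparison by arm is seen. Following Aim A:

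- **Section E.2, role.** State that effectiveness is judged on diabetes and hypertension and that HIV control is monitored. Remove viral load from the sentence on t-tests at 0.05.
- **Section E.2, HIV analysis.** Report HIV once, across all randomised participants with HIV-RNA data, as the arm difference in the percentage below 20 copies/mL with a 95% confidence interval, stratified by the randomisation factors (sex and comorbidity). Describe CD4 counts alongside, give the number with missing HIV-RNA in each arm, and make no effectiveness claim.
- **Section F.1.** State that the 22-per-group figure rests on an HIV outcome and does not establish power for diabetes or hypertension.

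If the sponsor instead wants HIV as an effectiveness outcome, Aim A must say so and HIV must enter a multiplicity procedure with the other two diseases (for example, 0.05/3 = 0.0167 each under Bonferroni).

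The cost is edits to two sections and one results table, with no new participants or data. The downside of following Aim A is that the sponsor gives up an HIV effectiveness claim that Aim A does not anticipate, and has to acknowledge that the displayed sample size does not address the two diseases in the aim.

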Medical records for both groups are necessary. As the study is designed to randomize sequentially after medical records are received, medical records will be sought for all those consented. This is a study validity requirement. As the information to determine disease improvement or worsening is only officially determined via medical records of the participant's healthcare provider, medical records must be obtained for both groups to compare groups. This is also why medical records will be sought throughout the study. The information extracted from the medical records and entered into the database will be primarily used to assess for differences between the groups. See the **Data Safety Monitoring Plan** (provided) for more details.

The layman's description of what specific information will be extracted and used from the medical records is provided in the consent form, following the header, "What information is being used from your medical records?" A more technical description is found in the database section that follows.

Walgreens study pharmacists will not be provided the actual medical records. For those participants randomized to intervention group, the medical records will be used to populate the **CASE REPORT FORMS for Pharmacist Use or CRF-Pharmacist**. Only the PI, SC (and [name] who is providing physician oversight to ensure accuracy, integrity and meaningfulness of extracted data being provided to the study pharmacist) will see the medical records. Only PI and SC will extract clinical data from the medical records for entry onto intervention group's participant's CRF-Pharmacist. This will occur every time medical records are received for participants randomized to the intervention group. Only the CRF-Pharmacist (not the actual medical records) will be provided to the Walgreens study pharmacist. The CRF-Pharmacist will be provided to the study pharmacist in advance of the MTM visit. CRF-Pharmacist will be hand carried in a secure container and provided to the study pharmacist. For those participants randomized to the control group, a case report form only containing the participant study UID number and other pertinent document header information will be provided to the study pharmacist.

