Information from the medical records for all participants will also be used to enter diseases, medications, laboratory results, and vital signs into the study database. More details are contained in the database section below. **SCREENSHOTS OF DATABASE** entry fields are provided to detail what information from the medical records and CRF is to be entered into the database. To clarify, only the PI/SC will enter data into this database. No study pharmacist or participants will ever engage with this database.

In summary, intervention group participants' initial and all subsequent CRF-Pharmacist given to the study pharmacist will have information extracted from the medical records. During the study, if additional medical records are received and contain information not previously included on the CRF-Pharmacist or update previously included information on the CRF-Pharmacist, this may result in more medical information being added to the CRF-Pharmacist. Control group participants CRF-Pharmacist will never have any information extracted from the medical records included. Recall the standard of care for MTM services is that the pharmacists do not have access to medical records directly from the patient's healthcare providers.

All originals of the CRF-Pharmacist and all medical records will remain at UNTHSC in a secured location (PI/SC offices) between study visits. A copy of the case report form will remain on site at the pharmacy in a secure location accessible only to study authorized Walgreens study pharmacists. Once randomized, the participant will be contacted to arrange an enrollment visit. The participant will be informed which group they were randomized to when contacted to arrange the enrollment visit. A script entitled, "**Follow up after consenting, medical records received and eligibility confirmed, to set up an enrollment visit at Walgreens pharmacy**" has been developed for this and is attached. If the participant expresses a desire to withdraw upon learning to which group s/he has been randomized, the participant will be reminded of the HIPAA release form and procedures to follow should they wish to no longer participate at that time. Participants will not be compensated for screening visits.

Within the main consent form, the participant will be asked to denote if the participant wishes for their HIV / primary care / specialist medical provider to be notified of their participation in this study.

Visit 2

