sample size computations shown above. We also conducted additional power analyses based on this sample size to verify that the analyses will be sufficiently powered when the outcome measures are treated as continuous (testing means) rather than dichotomous.

Control Group Medical Record Viewing by Study Pharmacist

Pharmacists are not prohibited from requesting the complete medical record from a medical provider pursuant to normal counseling and care provided, this is just rarely (if ever) done. Pharmacists routinely contact medical providers to recommend changes to medications. If the study pharmacist, in the course of providing MTM to participants in the control group, contacts a medical provider, this will not change the status of the control group participants. If, however, the study pharmacist feels compelled to obtain the entire medical record for a participant in the control group, s/he will notify the participant and PI/SC. Should the study pharmacist inadvertently gain access to a control participant's medical records (participant brings medical records themselves to the MTM session and the study pharmacist uses the complete medical record for the purposes of MTM), the participant will not be discontinued. In either case, the participant will not be discontinued. The time point at which the study pharmacist gained access to the medical record for participants in the control group will be noted and this will become a controlled variable in the analyses.

2) Describe both *Inclusion AND Exclusion Criteria*.

Inclusion criteria:

- >/= 18 years old or older at time of screening
- Male or female
- Self identifies as African-American or black
- Able to read and speak English sufficiently well enough to be interviewed by study pharmacist (as determined at screening visit by PI/SC)
- Confirmed diagnosis of HIV (medical record)
- Confirmed diagnosis of diabetes, hypertension, or both (medical record)
- Stated agreement to comply with study requirements during screening visit
- Able and willing to provide written informed consent
- Willing to notify study pharmacist if becomes pregnant during study
- Expresses a willingness to participate in all study-related assessments and adhere to study requirements
- Willing to notify research team if planning to relocate
- Willing to notify research team if incarcerated at any point during study

Exclusion criteria: (whether discovered at time of consent or after review of medical records)

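### Where A1c or systolic blood pressure is analysed as continuous, the planned t-test ignores a baseline value that is mostly already in hand, which gives up precision in cells of about 22 per arm

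*Combined protocol and SAP*

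**What the plan says.** - **Tests (Section E.2).** "Two sample t-test for continuous outcomes (viral loads) and chi-square for categorical outcomes (blood pressure under control or not) would be used", at the 0.05 level. No covariate is named.
- **Continuous analysis (Section F.1, Sample Size).** Further power work is reported to show that the analyses are "sufficiently powered when the outcome measures are treated as continuous (testing means) rather than dichotomous". No SD, difference or correlation is given.
- **Comparisons (Section F.1).** Arms are compared on health indicators at the last follow-up visit, within sex-by-disease groups. The requirement is 22 per group, with 25 recruited.
- **Baseline data (Section E.1, Screening visit).** "the study is designed to randomize sequentially after medical records are received". Information from the records "for all participants will also be used to enter diseases, medications, laboratory results, and vital signs into the study database".
- **The only covariate (Section F.1, Control Group Medical Record Viewing).** If the pharmacist gains access to a control participant's record, the time of access is noted and "this will become a controlled variable in the analyses".
- **Outcome wording.** Section A sets out "To investigate the change in control of diabetes and/or hypertension in adult African-Americans with HIV", judged by A1c and plasma glucose for diabetes and by "systolic blood pressure from medical records (hypertension) and these will be compared against nationally accepted standards for each condition". Section E.2 says of hypertension that a "decrease in systolic blood pressure reductions of 10 mmHG [or attainment of blood pressure goal] was selected as the primary measure". For diabetes, E.2 gives an A1c goal but names no primary measure.

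**The concern.** The measurement taken before randomisation is often the best single predictor of the final A1c or systolic pressure, and it cannot be affected by arm. Leaving it out of a comparison of means leaves between-patient variation in the error term. With about 22 per arm in each comparison, that variation is expensive. Enrolment closed in October 2022 and Section E.5 sets the last visits for 15 December 2023, so the sample cannot grow. The analysis is what can still be improved.

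A related matter is that Sections A, E.2 and F.1 leave room for several versions of each outcome: final value, change, at goal, or a 10 mmHg fall or goal. The adjusted analysis needs a fixed place among them. If the version were picked after seeing the data, the nominal 5% level would no longer hold.

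**Working it through.** **1. The plan's own figure.** Inputs from F.1: 85% against 45%, 80% power, 0.05 (two-sided assumed, since sidedness is not stated). The pooled-variance formula is n = [1.96·√(2·0.65·0.35) + 0.8416·√(0.85·0.15 + 0.45·0.55)]² / 0.40². This gives (1.322 + 0.515)² / 0.16 = 21.1, so 22 per group. It reproduces, but it concerns a binary HIV outcome and says nothing about the precision of continuous A1c or systolic pressure.

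**2. Assumptions for the continuous case.** The documents give no SD or correlation r. I assume a 10 mmHg between-arm difference (the 10 mmHg in E.2 is a within-patient fall), SD 18, 22 per arm, two-sided 0.05, and r = 0.3, 0.5 or 0.7.

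**3. Formulas.** Standard error = 18·√(2·V/22) = 5.427·√V. Noncentrality = 10 / standard error, and power comes from the noncentral t distribution.
- Final value: V = 1, 42 df.
- Change score: V = 2(1 − r), 42 df.
- Baseline-adjusted: V = (1 − r²)(1 + 1/39), 41 df. The factor 1 + 1/(2n − 5) charges for chance baseline imbalance in a small sample.

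| Analysis | r = 0.3 | r = 0.5 | r = 0.7 |
|---|---|---|---|
| Final value: noncentrality | 1.84 | 1.84 | 1.84 |
| Final value: power | 44% | 44% | 44% |
| Change score: noncentrality | 1.56 | 1.84 | 2.38 |
| Change score: power | 33% | 44% | 64% |
| Adjusted: noncentrality | 1.91 | 2.10 | 2.55 |
| Adjusted: power | 46% | 54% | 70% |
| Adjusted, 20% baselines missing, with indicator (simulated): power | 44% | 51% | 62% |

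The missing-baseline row assumes values missing at random with respect to arm. Its simulated type I error is about 5%.

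**4. Break-even.** Adjustment pays once (1 − r²)(40/39) < 1, that is r² > 1/40, or r above about 0.16 at 22 per arm.

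**5. Sensitivity (same formulas, adjusted power at r = 0.3/0.5/0.7).**
- SD 15: 58% unadjusted, 61/69/85% adjusted.
- SD 20: 37% unadjusted, 39/46/61% adjusted.
- SD 18, 30 per arm (assumed, because F.1 expects dual diagnoses to enlarge the groups): 56% unadjusted, 59/68/84% adjusted.
- SD 18, sexes pooled, 44 per arm: 73% unadjusted, 77/84/95% adjusted.
- A1c, assumed difference 1.0 and SD 1.5, 22 per arm: the ratio is 0.667, as for 10/15, so the SD 15 figures apply.

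**6. Choosing the version afterwards.** Under no effect, 40,000 simulated trials with 22 per arm and SD 18 gave these chances of at least one significant result:
- final-value or change t-test: about 9%;
- at goal, or 10 mmHg fall or goal, by chi-square: about 7%.

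The binary runs use a cut of 140 and baseline means of 140 and 145. These are illustrative only and are not in the documents.

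**The case against.** The strongest reply is that the precision gain misses the one primary measure that E.2 names. A 10 mmHg fall or attainment of goal reads as binary, blood pressure is the chi-square example, and viral load is the only t-test example. Continuous A1c or systolic pressure rests on the power remark in F.1. This stands. For the binary measure, a baseline-adjusted logistic model gained only 0 to 4 points of simulated power once its test was held to 5% size, so there is no case for replacing the chi-square.

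Second, the documents lean towards change (Section A speaks of change in control, and F.1 counts improvement). If change scores are intended, baseline already enters, and at r = 0.7 the gap is 64% to 70%, not 44% to 70%. This also stands. At r = 0.3, however, a change score does worse than ignoring baseline, while adjustment does not.

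Third, baselines may be old or absent. Records are requested for the 12 months before the latest provider visit, and eligibility requires a diagnosis, not a value. With 20% missing and r = 0.3 the gain is nil.

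A reader might infer that the stated tests are biased. The documents do not support that: randomisation protects the unadjusted comparison. Outcomes missing differently by arm could bias any of these tests, since E.1 keeps participants whose records never arrive, and adjustment is not offered as a cure. A reader might also infer that Sections A, E.2 and F.1 contradict each other outright. They can be read together as aim, measure and time point. The text is ambiguous, and no section plans a choice made after the fact.

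**Conclusion.** The point holds as a cheap improvement in precision, not as an error in the validity of the stated tests. No planned test uses baseline A1c or systolic pressure, although records precede randomisation in the Section E.1 procedures. (F.1 says more loosely that randomisation follows consent.)

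Under the assumed 10 mmHg difference and SD 18, adjustment adds about 2, 10 and 26 points of power over a final-value t-test at r = 0.3, 0.5 and 0.7. With a fifth of baselines missing, it adds about 0, 7 and 18. Against a change score at r = 0.7 it adds about 6 with complete baselines. It would be wrong to conclude that adjustment rescues the within-cell comparisons: at SD 18 and 22 per arm no adjusted figure reaches 80%.

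All sizes depend on assumed values of SD, r and missingness. The type I error of about 7 to 9% applies only if the outcome version is chosen after seeing the data. The separate data safety monitoring plan that the protocol cites is not among the documents and might say more.

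**What to change.** Before unblinded analysis, reconcile Sections A, E.2 and F.1 to the following.

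1. **Any continuous A1c or systolic pressure analysis:** replace the t-test with a linear regression of the final value on arm and the pre-randomisation value of the same measure, with a missing-baseline indicator. Add sex and diagnosis stratum if cells are pooled. State how old a baseline value may be.
2. **Hypertension:** keep the E.2 measure (10 mmHg decrease or attainment of goal) with the chi-square as primary. Label baseline-adjusted systolic pressure secondary.
3. **Diabetes:** make baseline-adjusted final A1c the single primary outcome, with A1c at goal and plasma glucose secondary.
4. **HIV:** viral load and CD4 count stay as monitoring measures, as Section A describes them.

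The cost is analysis-plan wording and a little more analysis work, with no new data collection. The downside is that some baselines will be old or missing, which shrinks the gain and at low correlation removes it.
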